### **3. Trial Objectives and Purpose**

To assess the acute safety and device procedural success of the Scoreflex NC scoring PTCA catheter in its intended use for the dilatation of coronary artery stenosis ( $\geq 70\%$  diameter stenosis).

### **4. Trial Design**

A prospective, open label, multi-center, single arm, observational study designed to evaluate the acute safety and device procedural success of the Scoreflex NC scoring PTCA catheter in subjects with stenotic coronary arteries during percutaneous coronary intervention.

Two-hundred (200) subjects will be treated at up to 15 U.S. sites with the Scoreflex NC catheter during their index procedure. All subjects will be screened according to the protocol inclusion and exclusion criteria and will be followed through hospital discharge.

#### **4.1 Selection and Withdrawal of Subjects**

Once the subjects have signed the Institutional Review Board (IRB) approved study informed consent form (ICF) and research authorization forms (RA/HIPAA) and have met all general inclusion and exclusion criteria, the subjects will be considered eligible to be enrolled in the study to receive treatment with the Scoreflex NC dilatation catheter. A subject is considered enrolled in the study upon insertion of the investigational device into a guide catheter. Upon enrollment, a subject identification number will be assigned to each subject in a consecutive manner within each clinical site.

#### **4.2 Inclusion Criteria**

##### **4.2.1 Clinical Inclusion Criteria**

- Subject is  $\geq 18$  years of age.
- Subject or a legally authorized representative must provide written informed consent prior to any study related procedures.

- Subject must agree not to participate in any other clinical study during hospitalization for the index procedure that would interfere with the endpoints of this study.
- Subjects must have a single or double vessel coronary artery disease and clinical evidence of ischemic heart disease, such as symptomatic CAD, stable / unstable angina or silent ischemia.

#### **4.2.2 Angiographic Inclusion Criteria**

- Subject must have *de novo* or restenotic lesion(s) in native coronary arteries, including in-stent restenosis that are suitable for percutaneous coronary intervention.
- A maximum of two lesions, including at least one target lesion, in up to two coronary arteries.
- Target lesion must have a reference vessel diameter (RVD) between 1.75 and 4.0 mm by visual estimation.
- Target lesion(s) must have a diameter stenosis of  $\geq 70\%$  by visual estimation and may include chronic total occlusions (CTO)
- The non-target lesion must be located in different coronary artery from the Target lesion.
- Treatment of non-target lesion, if any, must be completed prior to treatment of target lesion and must be deemed a clinical angiographic success as visually assessed by the physician.

### **4.3 Exclusion Criteria**

#### **4.3.1 Clinical Exclusion Criteria**

- Subject with a known hypersensitivity or contraindication to aspirin, heparin, bivalirudin, anti-platelet medications, or sensitivity to contrast media, which cannot be adequately pre-medicated.
- Subject with known diagnosis of STEMI or NSTEMI at index presentation or within 7 days of study screening.
- Subject with known pregnancy or is nursing. Women of child-bearing potential should have a documented negative pregnancy test within 7 days before index procedure.
- Planned or actual target lesion treatment with an unapproved device, atherectomy, laser, cutting balloon or thrombectomy during the index procedure.
- A serum creatinine level  $> 2.0$  mg/dl within seven days prior to index procedure.
- Cerebrovascular accident (CVA) within the past 6 months.
- Active peptic ulcer or active gastrointestinal (GI) bleeding within the past 6 months.
- Subject has a known left ventricular ejection fraction (LVEF)  $< 30\%$  (LVEF may be obtained at the time of the index procedure if the value is unknown, if necessary)

- Target lesion located within an arterial or saphenous vein graft or graft anastomosis

#### **4.3.2 Angiographic Exclusion Criteria**

- More than two lesions requiring treatment.
- Target lesion longer than 30 mm by visual estimation.
- Extreme angulation (90° or greater) proximal to or within the target lesion.
- Previous percutaneous intervention of lesions in a target vessel (including side branches) conducted within 9 months before the study procedure and located within 10 mm from the current target lesion.
- Target lesion demonstrating severe dissection prior to planned use of the Scoreflex NC device
- Unprotected left main coronary artery disease. (Greater than 50% diameter stenosis)
- Coronary artery spasm of the target vessel in the absence of a significant stenosis.
- Target lesion with angiographic presence of probable or definite thrombus.
- Target lesion involves a bifurcation requiring treatment with more than one stent or pre-dilatation of a side branch >2.0 mm in diameter.
- Non-target lesion to be treated during the index procedure meets any of the following criteria:
  - Located within a bypass graft (venous or arterial)
  - Left main location
  - Chronic total occlusion
  - Involves a bifurcation (e.g., bifurcations requiring treatment with more than 1 stent)
  - Treatment not deemed a clinical angiographic success.

#### **4.4 Subject Withdrawal Criteria**

Each enrolled subject shall remain in the study until completion of the required follow-up period, however, a subject's participation in any clinical study is voluntary and the patient has the right to withdraw at any time without penalty or loss of benefit. Conceivable reasons for discontinuation may include, but not be limited to, the following:

- Subject death
- Subject voluntary withdrawal
- Subject withdrawal by physician as clinically indicated
- Subject lost-to follow-up

The reason for subject discontinuation must be documented on the CRF and source documents. The Primary Investigators must also report all subject discontinuations to their IRB, MEC, or HREC as defined by their Institution's procedure.

## 5 Treatment of Subjects

A maximum of two lesions, including at least one target lesion, may be treated during the index procedure.

Non-target lesion should be treated first and deemed a clinical angiographic success by visual assessment prior to treatment of the target lesion.

The lesion identified as the Target lesion is intended to be treated during the index procedure with a Scoreflex NC study device.

### 5.1 Non-Target Lesion

- A maximum of one non-target lesion (in addition to one target lesion in a target vessel) may be treated in a non-target vessel with a commercial treatment during the index procedure and must be completed prior to treatment of target lesion.
- Treatment of non-target lesion must be deemed a clinical angiographic success as visually assessed by the physician for subjects to be eligible for enrollment into the study.
- Target and non-target lesions must be located in different coronary arteries.

### 5.2 Target Lesion

- Lesion that is to be treated with the Scoreflex NC study device during the index procedure.
- Target lesions (maximum of 2) may be located in the same or different coronary arteries.
- Target lesion composed of multiple focal lesions that can be covered with one stent will be considered as a single lesion.
  - *Note:* A separate Scoreflex NC study catheter must be used for treatment of each target lesion, if there is more than one target lesion identified to be treated.

**Table 1.0 Schedule of Procedures**

	≤ 7 Days before procedure	≤ 24 hours before procedure	Procedure	Post-procedure / Hospital Discharge
Study Eligibility	X			
Informed consent	X			
Demographics, Medical history including coronary medical history	X			
Physical assessment, including vital signs	X			X
Angina class	X	X		X
12-lead ECG		X		X
Cardiac Medication review		X	X	X
Pregnancy test (women only)	X			
Laboratory Tests				
Serum Creatinine	X			
CBC with platelets	X			
CK Total/ CK-MB		X a	X b	X
Angiographic Assessment			X	
Review of Adverse events and device-related events			X	X

- a. All subjects must have CK/CK-MB drawn within 24 hours before the procedure to determine eligibility; however, if the results are not available, eligibility may be based upon troponin values.
- b. For three CK-MB draws. The first draw should be performed immediately after the procedure, the second draw should be performed 6-12 hours post-procedure and the third draw should be performed 18-24 hours post-procedure, or prior to discharge, whichever comes first.

### 5.3 Study procedures

#### 5.3.1 Written Informed Consent

Written informed consent must be obtained prior to initiation of any study-related procedures that are performed solely for the purpose of determining eligibility to participate in the study. Once the subjects have signed the Institutional Review Board (IRB) approved study informed consent form (ICF) and research authorization forms (RA/HIPAA) and have met all general inclusion and exclusion criteria, the subjects will be considered eligible to be enrolled in the study to receive treatment with the Scoreflex NC investigational device. A subject is considered enrolled in the study upon

insertion of the investigational device into a guide catheter. Upon enrollment, a subject identification number will be assigned to each subject in a consecutive manner within each clinical site. The site enrollment log should be completed with the subject enrollment information.

### **5.3.2 Up to 7 days Prior to Index Procedure**

The following pre-procedure data (specific data is noted in the eCRF) must be collected within 7 days prior to the index procedure for all subjects:

- Review of Inclusion and Exclusion criteria
- Demographics, Medical history including coronary medical history
- Angina class
- Laboratory tests:
  - Serum Creatinine
  - CBC with platelets
  - Pregnancy test for females of child-bearing potential with analysis per local practice (serum and/or urine)

### **5.3.3 Within 24 hours Prior to Index Procedure**

The following pre-procedure data must be collected within 24 hours prior to the index procedure for all subjects:

- Current antiplatelet, anti-thrombotic and cardiac medications
- 12-lead electrocardiogram (ECG)
- Laboratory tests:
  - Cardiac enzymes: CK Total and, if CK Total is abnormal ( $>1x$  ULN), CK-MB must be performed.
  - If CK/CK-MB results are not available; eligibility may be based upon troponin values.

Note: CK/CK-MB must be drawn prior to the index procedure; however if the results are not available, eligibility may be based upon troponin values.

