#### **Cardiac enzyme collection requirements:**

- For subjects who present with Stable Angina or Silent Ischemia:
  - CK/CK-MB must be drawn prior to the index procedure.
  - The results of the enzyme testing are not required to be available prior to the index procedure.

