### 6.2 Secondary endpoints

The following secondary Angiographic Procedural efficacy endpoint will be measured:

- Final diameter stenosis  $\leq 50\%$  in at least one of the Scoreflex NC attempted lesions following completion of the interventional procedure, including adjunctive stenting

The following secondary clinical endpoints will be measured through hospital discharge:

- In-hospital Major Adverse Cardiac Events (MACE), a composite of:
  - All death (cardiac and non-cardiac)
  - Myocardial infarction (MI)
  - Target Lesion Revascularization (TLR), clinically indicated
- In-hospital stent thrombosis (ST) within the target vessel
- Clinically significant arrhythmias (requiring intervention)

The following secondary peri-procedural endpoints will be measured through hospital discharge:

- Occurrence of Scoreflex NC study balloon rupture

- Improvement in Minimum Lumen Diameter (MLD) following use of Scoreflex NC coronary dilatation catheters (measured by QCA)

Both MI and ST are to be determined by the Academic Research Consortium (ARC) classification criteria. MI to be classified into various types and include the 99th percentile upper reference limit (URL) decision limits for biomarkers employed.

Myocardial Infarction will be defined as:

- Q-Wave MI: Development of new (i.e., not present on the subject's ECG before allocation) pathological Q-waves in 2 or more leads lasting 0.04 seconds with post-procedure CK-MB levels elevated above normal.
- Non-Q-Wave MI: Elevation of post-procedure CK-MB levels to >3.0 times ULN without new Q-waves.

For subjects undergoing bypass surgery, a peri-operative MI will be defined as follows:

- a) Total CK-MB >5× ULN.  
or
- b) Presence of new pathologic Q-waves as defined above.

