6.2.2. Secondary Endpoints

The secondary endpoints consist of angiographic procedural efficacy, clinical, and peri-procedural endpoints.

The secondary angiographic procedural efficacy endpoint is measured and defined as follow:

- Final diameter stenosis $\leq 50\%$ in at least one of the Scoreflex NC attempted lesions following completion of the interventional procedure, including adjunctive stenting

The secondary clinical endpoints which are measured through hospital discharge are as follows:

- In-hospital Major Adverse Cardiac Events (MACE), a composite of the following:
 - All death (cardiac and non-cardiac)
 - Myocardial infarction (MI)
 - Clinically indicated Target Lesion Revascularization (TLR)
- In-hospital stent thrombosis (ST) within the target vessel
- Clinically significant arrhythmias (requiring intervention)

The secondary peri-procedural endpoints are measured through hospital discharge and defined as follows:

- Occurrence of Scoreflex NC study balloon rupture
- Improvement in Minimum Lumen Diameter (MLD) following use of Scoreflex NC coronary dilatation catheters (measured by QCA)

Both MI and ST are to be determined by the Academic Research Consortium (ARC) classification criteria. MI will be classified into various types including the 99th percentile upper reference limit (URL) decision limits for biomarkers employed.

Myocardial Infarction will be defined as:

- Q-Wave MI: Development of new (i.e., not present on the subject's ECG before allocation) pathological Q-waves in 2 or more leads lasting 0.04 seconds with post-procedure CK-MB levels elevated above normal.
- Non-Q-Wave MI: Elevation of post-procedure CK-MB levels to >3.0 times ULN without new Q-waves.

For subjects undergoing bypass surgery, a peri-operative MI will be defined as follows:

a) Total CK-MB $>5\times$ ULN.

or

b) Presence of new pathologic Q-waves as defined above.

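### The non-Q-wave MI rule ignores the pre-procedure CK-MB, so a pre-existing elevation can count as an in-hospital MI and MACE; the protocol is also inconsistent on whether every subject has that baseline

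*Protocol*

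**What the plan says.** **MI definition.** SAP 6.2.2 reads "Non-Q-Wave MI: Elevation of post-procedure CK-MB levels to >3.0 times ULN without new Q-waves", and protocol 6.2 uses the same definition. Neither mentions the pre-procedure CK-MB. The Q-wave limb beside it does ask for change: the waves must be new, that is "not present on the subject's ECG before allocation". Both sections also state that "Both MI and ST are to be determined by the Academic Research Consortium (ARC) classification criteria" and refer to 99th percentile limits for the biomarkers. Neither says how those criteria fit with the 3 times ULN rule. MI is a component of in-hospital MACE.

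**Baseline draw.** Four places in the protocol bear on it:

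- The laboratory list in 5.3.3 asks for "CK Total and, if CK Total is abnormal" (above 1 times ULN), CK-MB.
- The Note in 5.3.3 says "CK/CK-MB must be drawn prior to the index procedure; however if the results are not available, eligibility may be based upon troponin values".
- Footnote a of the Schedule of Procedures says "All subjects must have CK/CK-MB drawn within 24 hours before the procedure to determine eligibility", also with troponin as the fallback.
- The paragraph on cardiac enzyme collection, for stable angina or silent ischemia, requires CK/CK-MB to be drawn but adds that "The results of the enzyme testing are not required to be available prior to the index procedure".

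**Eligibility and adjudication.** Unstable angina is eligible (protocol 4.2.1). Protocol 4.3.1 excludes a known STEMI or NSTEMI at presentation or within 7 days of screening. No criterion in 4.2 or 4.3 contains an enzyme cut-off. An independent CEC adjudicates clinical endpoints with definitions that must agree with the investigational plan (protocol 6.4).

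**The concern.** One limb of the MI definition measures change and the other measures a level. The study's objective is acute safety, and in-hospital MACE is its composite clinical measure. If a level alone suffices, an elevation that predates the device can enter the MI and MACE counts. The error runs in one direction, against the device.

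Whether it can be put right afterwards depends on whether the subject's own baseline CK-MB exists, and the protocol gives two answers to that. With few MACE expected in 200 subjects, one or two misclassified cases would visibly change the reported rate.

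**Working it through.** The plan gives no figure to reproduce: the sample size of 200 is stated not to rest on a hypothesis, and no MI or MACE rate is assumed. The check is therefore of the text, followed by an illustration of size.

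**1. What the rule does.** Let B be the pre-procedure CK-MB and P the highest post-procedure CK-MB, both in multiples of ULN. With no new Q-waves, the written rule is MI if P > 3.

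- B at or below 1, P above 3: a new elevation, counted as intended.
- B between 1 and 3, P above 3: a rise occurred after a raised baseline. It is counted, and the plan does not say whether it should be.
- B above 3, P above 3 but no higher than B: no rise, yet counted.

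The third case is the clear misclassification. It arises because the rule does not use B, and it arises even when B was measured.

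**2. When B is available.**

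| Total CK before procedure | 5.3.3 laboratory list | Note in 5.3.3, enzyme paragraph, footnote a |
|---|---|---|
| Above 1x ULN | CK-MB measured | CK/CK-MB drawn |
| Normal | CK-MB not required | CK/CK-MB drawn |

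The texts differ only in the second row, and the combined term CK/CK-MB is itself ambiguous. A missing baseline is therefore limited to subjects with normal total CK at sites that follow the conditional line.

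**3. Can a subject with raised CK-MB enter?** Footnote a ties the draw to eligibility, but the criteria give no threshold. The barrier is a known STEMI or NSTEMI. In stable angina or silent ischemia the result may still be outstanding when the subject is enrolled. Entry is possible; the documents do not show how often it would happen.

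**4. Size, by assumption.** Each misclassified subject who has no other MACE adds 1/200 = 0.5 percentage points.

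For scale, the predecessor-device trial in protocol 2.6.1 reports 6 subjects with in-hospital MACE: 6/263 = 2.3% of those enrolled, or 6/238 = 2.5% of the clinical-success denominator. I take 5/200 = 2.5% as an assumed true rate. Exact 95% limits for x events in n = 200 are the 0.025 quantile of Beta(x, n − x + 1) and the 0.975 quantile of Beta(x + 1, n − x).

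| False MIs added | MACE | Rate | Exact 95% CI |
|---|---|---|---|
| 0 | 5/200 | 2.5% | 0.8 to 5.7% |
| 1 | 6/200 | 3.0% | 1.1 to 6.4% |
| 2 | 7/200 | 3.5% | 1.4 to 7.1% |
| 4 | 9/200 | 4.5% | 2.1 to 8.4% |
| 6 | 11/200 | 5.5% | 2.8 to 9.6% |

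If a share q of subjects is affected, the expected number is 200q and the chance of at least one is 1 − (1 − q)^200. For q = 0.5%, 1%, 2% and 3% the expected numbers are 1, 2, 4 and 6, and the chances are 63%, 87%, 98% and 99.8%. The documents give no value of q, so these rows show sensitivity and are not a forecast.

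**The case against.** A reader might infer that baseline CK-MB is measured only when total CK is abnormal, and that pre-existing elevations are therefore scored as MI. The documents do not support that, for three reasons.

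- The conditional line is one of four statements; the other three carry no such condition.
- The causal step fails. Even under the conditional line, a subject with raised total CK has a baseline CK-MB. The misclassification comes from a rule that does not use the baseline. The conditional draw only limits later correction, and only for subjects with normal total CK.
- Saying that such a subject will be scored is too strong. Known STEMI and NSTEMI are excluded, the ARC criteria are also invoked, and a CEC adjudicates under a charter that is not among the documents. How the ARC criteria treat a raised baseline is not reproduced in the plan.

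It is also fair to say that MACE is a secondary endpoint, reported descriptively with no test or performance goal, and that one or two false events shift the rate by far less than the width of its confidence interval.

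These objections limit the claim to what can happen, and they make a large effect unlikely. They do not remove the gap. The CEC is tied to the plan's definitions, the only numerical non-Q-wave rule in the plan has no baseline term, and the plan does not say whether that rule or ARC governs. Sampling width does not excuse an avoidable error that runs in one direction.

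**Conclusion.** The point holds in two parts. First, the non-Q-wave rule is an absolute post-procedure threshold, so on its literal reading a pre-existing CK-MB elevation can be counted as an in-hospital MI and MACE. Second, and separately, the protocol contradicts itself on whether every subject has a baseline CK-MB; where one is absent, an old elevation cannot be separated from a new one.

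The size is 0.5 percentage points of MACE per affected subject at N = 200. The number of affected subjects is unknown and probably small given the STEMI/NSTEMI exclusion. The assumed 2.5% true rate and the assumed values of q serve only to show scale. The primary endpoint does not use CK-MB and is unaffected.

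**What to change.** 1. In protocol 6.2, SAP 6.2.2 and the CEC charter alike, require that post-procedure CK-MB exceed 3 times ULN and, when the subject's pre-procedure value was already above ULN, that it also represent a rise over that value. State how large a rise counts; otherwise a step from 3.1 to 3.2 times ULN would still qualify. Changing the SAP alone would leave it at odds with the protocol to which the CEC is bound.
2. State whether the ARC criteria or the 3 times ULN rule governs, and how a subject with no baseline CK-MB is classified.
3. Reconcile the laboratory list and Note in protocol 5.3.3, the enzyme-collection paragraph and footnote a of the schedule on the baseline CK-MB draw.
4. Beside the MACE rate, report the number of subjects and of MIs with a raised baseline CK-MB and with a missing one. SAP Table 4 or Table 13.2 could carry this.

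The cost is a few sentences in the protocol, SAP and charter, and one table row. SAP section 12 already provides for an amended SAP before the primary endpoint is analyzed. SAP section 7 describes data collection in the past tense; if enrollment is over, missing baselines cannot be recovered, but items 1, 2 and 4 remain possible. If events have already been adjudicated under the literal rule, MACE should be shown both ways.

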#### **Cardiac enzyme collection requirements:**

- For subjects who present with Stable Angina or Silent Ischemia:
  - CK/CK-MB must be drawn prior to the index procedure.
  - The results of the enzyme testing are not required to be available prior to the index procedure.

### **5.3.4 Index Procedure**

The start of the index procedure is defined as the time of sheath insertion. If a previously placed sheath is used (i.e., from an earlier diagnostic procedure), index procedure start time is defined as the time of guide catheter insertion into sheath for wiring the target lesion. During cardiac catheterization, the following procedures and assessments must be completed.

- Perform angiography according to the Angiographic Core Laboratory procedure guidelines.
- Confirm angiographic eligibility criteria.
- Treat the non-target lesion, if any, prior to treatment of the target lesion as described in Section 6.1.
- If treatment of non-target lesion was successful, continue with enrolling the subject in the study.
- If the subject is enrolled, treat subject accordingly with the Scoreflex NC catheter and perform angiography according to the Angiographic Core Laboratory procedure guidelines and collect study related data.
- If more than one lesion is treated with the Scoreflex NC catheter, similarly perform angiography according to the Angiographic Core Laboratory procedure guidelines and collect study related data.

